The subjects will be identified/recruited during clinic hours as patients requiring an elective or traumatic foot and ankle surgery. During the clinic hours the primary investigator and/or the co-investigator will obtain full consent from the patient. We will recruit a minimum of 115 participants into each of two study arms, an immediate weight-bearing arm and a non-weight-bearing arm, so 230 participants will be included. Patients will be eligible if they are undergoing elective or traumatic foot and ankle surgery. Exclusion criteria will include any patient less than 18 years of age & over 89, history of foot or ankle surgery on the surgical limb, any degree of diagnosed peripheral neuropathy or peripheral vascular disease, infection, and/or unwillingness to participate at random in one of the two study arms.

Study Interventions and Measures:

We will be assessing the difference in two groups; immediate protected weight-bearing in a CAM walking boot vs strict non-weight-bearing for 6 weeks following foot and ankle surgery. Monitoring will be done by way of clinical follow-up, serial radiographs and/or other appropriate imaging modalities, and patient reported outcomes by way of AOFAS and SF-36 surveys.

Surgical procedures performed on patients included in the study will vary, as will the outcome measures for each procedure. Osseous fusions, including both elective joint fusions and bone healing following trauma, will be assessed by both clinical and radiographic evaluation. Soft tissue procedures, including elective stabilization and traumatic soft tissue repairs, will be assessed clinically and with imaging modalities

deemed appropriate. Complications during the perioperative and post-operative periods, such as non-union, infection, etc. will be included in the outcomes. All participants will also complete AOFAS and SF-36 surveys in the pre-operative and post-operative periods. We will also include return to work, activity, sport, etc. where appropriate.

Study Phase	Screening	Surgery	Post-op 2-3 w	Post-op 6-8 w	Post-op 3 m	Post-op 6 m	Post-op 1 yr	Post-op 2 yr	Unscheduled Visits
Visit Number	1		2	3	4	5	6	7	
Informed									
Informed Consent/Assent	x								
Review Inclusion/Exclusion									
Criteria	х								
Randomization	x								
Demographics/PMH	x								
Physical Examination	x		x	x	x	x	x	x	x
Adverse Event Assessment			x	x	x	x	x	x	x
Radiographs/Imagining	х		x	x	x	x	x	x	x
Complete AOFAS/SF- 36 survey	x			x	x		x	x	

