5.1.3 Radiographic/Advanced Imaging

X-rays, CT, MRI, and/or ultrasound will be obtained, when indicated, at certain visits determined by the physician. These imaging modalities will evaluate bone healing, joint fusion, and soft tissue repair integrity.

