6.2 Secondary Endpoints

The secondary outcome measures are the frequency of complications during the perioperative and post-operative periods, osseous healing as assessed by both clinical and radiographic evaluation, and healing outcomes of soft tissue procedures. These results will be analyzed at the end of the follow-up period.

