6.4 Statistical Methods

6.4.1 Analysis of Primary Outcome of Interest

All analysis will begin with assessment of the normality of continuous variables using the Kolmogorov-Smirnov test. Normally distributed continuous variables will be reported as means and standard deviations; non-normally distributed data as median and interguartile range. Categorical data will be reported as counts and percentages. The Student's t-test will be used to compare continuous demographic and clinical data between the immediate weight-bearing and non-weight-bearing groups. The chi-square test or Fisher's exact test will be used to compare categorical data between groups. Cronbach's alpha will be used to measure reliability, or internal consistency, of both the Medical Outcomes Study 36-Item Short Form Health Survey (SF-36) and the AOFAS Ankle-Hindfoot Scale survey (AOFAS). Spearman's rank correlation coefficient will be used to assess the relationship between the physical and mental component scores and the eight subdomain scores from the SF-36 and the pain, function and alignment scores of the AOFAS. SF-36 scores and AOFAS scores will be adjusted for patient age, gender, BMI and presence of diabetes mellitus. Nonparametric tests will be used when data breaks the normality assumption. A value of p<.05 on twotailed testing will be considered statistically significant. Statistical analysis will be performed using IBM-SPSS Statistics, version 24.0 (IBM-SPSS Inc., Armonk, NY). Using one-way repeated measures analysis of variance (ANOVA), differences over time in radiographic and advanced imaging parameters will be assessed separately for the immediate weight-bearing and non-weight-bearing groups. Two-way repeated measures ANOVA will be used to assess differences over time in these parameters between the two groups. Tukey's test or Dunn's procedure will be used for post-hoc pairwise comparisons, as indicated.

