Descriptive statistics on the physical and mental component scores and the eight subdomain scores from the SF-36 will be reported for the immediate weight-bearing and non-weight bearing groups. In order to examine differences in SF-36 scores within each group over time, a one-way repeated measures ANOVA will be conducted to determine if the SF-36 scores are significantly different between visits (e.g., screening, post-operative at 6-8 weeks, post-operative at 12 months, and post- operative at 24 months). A two-way repeated measures ANOVA will be conducted to determine if the SF-36 scores are significantly be conducted to determine if the SF-36 scores are significantly be conducted to determine if the SF-36 scores are significantly be conducted to determine if the SF-36 scores are significantly be conducted to determine if the SF-36 scores are significantly be conducted to determine if the SF-36 scores are significantly be conducted to determine if the SF-36 scores are significantly be conducted to determine if the SF-36 scores are significantly different between the two groups for these same visits. Post-hoc pairwise comparisons using Tukey's test or Dunn's procedure will be performed, as indicated.

Descriptive statistics on the pain, function and alignment component scores from the AOFAS will be reported for the immediate weight-bearing and non-weight bearing groups. In order to examine differences in AOFAS scores within each group over time, a one-way repeated measures ANOVA will be conducted to determine if the AOFAS scores are significantly different between visits (e.g., screening, post-operative at 6 – 8 weeks, post-operative at 12 months, and post-operative at 24 months). A two-way repeated measures ANOVA will be conducted to determine if the AOFAS scores are significantly different between visits. Post-hoc pairwise comparisons using Tukey's test or Dunn's procedure will be performed, as indicated.

The chi-square test will be used to examine the frequency of complications during the perioperative and post-operative periods, osseous healing as assessed by both clinical and radiographic evaluation and frequency of soft tissue procedures between the immediate weight-bearing and non-weight bearing groups.

Logistic regression analysis will be performed to assess which patient characteristics and surgical characteristics are associated with higher SF-36 scores and AOFAS scores.

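### The repeated measures ANOVA planned for imaging has no numeric parameter common to all patients, and soft tissue healing has no test of its own

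*Combined protocol and SAP*

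**What the plan says.** Section 6.4.1 gives imaging two analyses. By one-way repeated measures ANOVA, "differences over time in radiographic and advanced imaging parameters will be assessed separately for the immediate weight-bearing and non-weight-bearing groups". Then, for the comparison of arms, "Two-way repeated measures ANOVA will be used to assess differences over time in these parameters between the two groups". No parameter, unit, modality or visit set is named.

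The content of the imaging is described elsewhere:

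- Section 5.1.3: "These imaging modalities will evaluate bone healing, joint fusion, and soft tissue repair integrity". The same section says that X-ray, CT, MRI and/or ultrasound "will be obtained, when indicated, at certain visits determined by the physician".
- Abstract, Study Interventions and Measures: "Surgical procedures performed on patients included in the study will vary, as will the outcome measures for each procedure". On tendon and ligament work it adds: "Soft tissue procedures, including elective stabilization and traumatic soft tissue repairs, will be assessed clinically and with imaging modalities", the choice of modality being left to what is thought suitable.
- Section 6.2 lists among the secondary endpoints "osseous healing as assessed by both clinical and radiographic evaluation, and healing outcomes of soft tissue procedures".

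Later in 6.4.1 there is a categorical comparison: "The chi-square test will be used to examine the frequency of complications during the perioperative and post-operative periods, osseous healing". That sentence ends with how often soft tissue procedures occur in each arm, not with how they healed.

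**The concern.** A two-way repeated measures ANOVA needs one quantitative variable, on one scale, in every patient, at a common set of visits. The trial enrols a wide mix of operations, from joint fusions and fracture fixation to tendon repair. Their imaging answers different questions, and no shared numeric scale is defined.

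An analyst who follows 6.4.1 must choose the variable, its coding and the patients it applies to after the data are in, or pool measurements that do not mean the same thing. Images taken only when judged necessary would also leave gaps, and classical repeated measures ANOVA drops a patient with an incomplete visit set.

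Structural healing is a central safety question for immediate weight-bearing: non-union, hardware failure and failed soft tissue repair are among the risks named in 6.8 and 7.3.2. The comparison of healing over time should therefore be one that can be carried out.

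**Working it through.** **1. The plan's own figure.** The only sample size calculation is for the questionnaires (6.5): d = 0.40, two-sided 0.05, 80% power, 100 evaluable per arm. By the normal approximation, n = 2(1.960 + 0.842)²/0.40² = 98.1, rounded up to 99. The t-test version gives 99.1, rounded up to 100, with power 80.4% at 100 per arm. Adding 15 per arm gives 115, or 230 in total. The figure reproduces. It says nothing about imaging, for which no power is stated.

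**2. Does the trial supply what the ANOVA needs?**

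| Requirement | What the documents give |
|---|---|
| A numeric variable | None defined. 5.1.3 and 6.2 describe healing, fusion and integrity without unit or score. The first intermetatarsal angle and first ray elevation appear only in 1.2, as outcomes of a cited study. |
| One scale for all patients | The abstract says that outcome measures differ by procedure. The form's list runs from 1st MPJ fusion through Achilles repair to TAR. |
| One modality | Four are possible (5.1.3). |
| Common visits | Table 1 and 4.3 put imaging at every follow-up visit; 5.1.3 makes it depend on indication and on the physician. These passages conflict and must be reconciled. |

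None of the four requirements is met for a whole-arm analysis.

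**3. What remains if the ANOVA is removed?**

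- Osseous healing: a chi-square test between arms (6.4.1). The plan thus already treats this outcome as categorical. The sentence names no visit.
- Soft tissue healing: listed as an endpoint in 6.2, but the matching part of the chi-square sentence tests the frequency of the procedures. Only the general rule in 6.4.1 that categorical data go to chi-square or Fisher's exact test is left.

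**4. How large a replacement model can the data carry?** Non-union in the fusion series cited in 1.2 runs from 0 (several series with complete union) to 2 of 22 (9.1%). Assume, as an upper limit, that all 100 evaluable patients per arm had bone procedures. Then 0 to 100 × 0.091 ≈ 9 patients per arm would be un-united at a late visit. With six post-operative visits, a model with arm (1 term), visit (5) and arm-by-visit (5) already has 11 terms besides the intercept, before any procedure group. At late visits the interaction terms might not be estimable.

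**5. Power of a single-visit comparison, under assumed failure rates.** With n = 100 per arm, power = Φ{[|p₂ − p₁|√n − 1.960√(2p̄(1 − p̄))] / √[p₁(1 − p₁) + p₂(1 − p₂)]}. Apart from 9.1%, the rates are assumptions.

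| p₁ | p₂ | Power |
|---|---|---|
| 2% | 10% | 67% |
| 5% | 15% | 66% |
| 9.1% | 15% | 25% |
| 9.1% | 20% | 59% |
| 9.1% | 25% | 85% |

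For 5% against 15%: (1.000 − 1.960 × 0.4243)/0.4183 = 0.403, and Φ(0.403) = 0.656. The real numbers per tissue type will be smaller than 100 per arm, so the comparison can be made but is not powered for modest differences.

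**The case against.** The best defence is that the plan separates two things: osseous healing goes to chi-square, while the unnamed parameters going to ANOVA may be angles or gaps, as in the cited literature. On that reading the defect is only a missing definition. Part of this stands, since the documents do not say on what scale imaging is read. But an angle is shared only by patients with the same kind of procedure, and the end of 6.4.1 makes any single-procedure analysis exploratory. A definition alone would not give the whole-arm ANOVA a variable to run on. The fallback to nonparametric tests in 6.4.1 does not help either: it deals with a defined variable that is not normal.

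It is also fair to say that osseous healing already has a between-arm test and that categorical data have a general rule. Both points stand and limit the finding.

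Two stronger readings are tempting. A reader might infer that every imaging outcome is a binary healed or not-healed judgement put wrongly into an ANOVA, so that unequal variances make it invalid. The documents do not support this: no coding is stated, and nothing says that union will be scored 0/1 for ANOVA. A reader might also infer that the trial has no usable between-arm comparison of imaging at all. The chi-square for osseous healing, which uses radiographic as well as clinical evaluation, contradicts that.

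**Conclusion.** The point holds for the pooled imaging ANOVAs, within and between arms: as written they cannot be carried out in a meaningful way, because no numeric parameter common to all patients is defined and the described outcomes differ by procedure, modality and timing. The plan thereby loses its only longitudinal between-arm imaging comparison. A second gap is that soft tissue healing has no specific test.

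Severity is moderate. Section 2.1 names imaging among the means of judging the primary objective, and a reader might conclude that the main result is at risk. It is not: 6.1 makes AOFAS and SF-36 the primary endpoints, 6.5 powers the trial on them alone, and healing is secondary in 6.2.

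The conclusion rests on the text supplied. The data form is only partly legible, so nothing here depends on whether its imaging lines are free text. No split of patients by tissue type is assumed: the form lists procedures rather than patients, and leaves some abbreviations unexplained.

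**What to change.** 1. In 6.4.1, delete the one-way and two-way repeated measures ANOVAs on whole-arm imaging.
2. Record a coded status at the scheduled imaging visits: united, partial or not united for bone; intact or not intact for soft tissue. State the criteria for each category. Reconcile 5.1.3 with Table 1 and 4.3, so that it is clear which images are expected when.
3. Compare arms within each tissue type at one visit named in advance, by chi-square or Fisher's exact test.
4. As a supporting longitudinal analysis, fit a simple repeated binary or ordinal model with arm and visit, only where event counts allow. Given the counts above, do not commit to arm-by-visit and procedure-group terms.
5. Correct the chi-square sentence so that it tests the soft tissue healing outcomes of 6.2.
6. Keep numeric measures such as angles for the procedures that share them, as exploratory results.

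The cost is revised wording and a coded field on the form, with slight extra data entry. It is best done before data are collected, since uncoded findings may be hard to classify consistently later. The sample size does not change. The healing comparison will have limited power, which the report should state.

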3.2.1 Duration of Study Participation

The study duration will require 7 visits to the clinic plus a surgery day therefore will require a pre-surgical visit/screening, surgery procedural day and six outpatient post-operative visits to the clinics. The entire follow up period will occur over 2 years.

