4.5.1 Early Termination Study Visit

Subjects who withdraw from the study before the 12 month follow-up visit will not be included in the final analysis of the study.

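### The SF-36 arm comparison by repeated measures ANOVA through 24 months would drop any subject with an incomplete set of scores at every visit, including late leavers whom section 4.5.1 does not exclude, and no other method is named for them

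*Combined protocol and SAP*

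**What the plan says.** Section 4.5.1 sets the only analysis-set rule in the documents: "Subjects who withdraw from the study before the 12 month follow-up visit will not be included in the final analysis of the study". It says nothing about subjects who leave between 12 and 24 months.

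Section 6.4.1 plans a one-way repeated measures ANOVA of SF-36 within each arm. The visits, introduced as examples, are screening, 6-8 weeks, "post-operative at 12 months, and post- operative at 24 months". A two-way repeated measures ANOVA then tests whether SF-36 scores "are significantly different between the two groups for these same visits". AOFAS has the same visit list, but its sentence does not name the arms: "A two-way repeated measures ANOVA will be conducted to determine if the AOFAS scores are significantly different between visits". The end of 6.4.1 says the primary analysis focuses on comparing the two weight-bearing groups.

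On software: "Statistical analysis will be performed using IBM-SPSS Statistics, version 24.0". No procedure within SPSS is named. The documents contain no imputation, mixed model or missing-data sensitivity analysis. Section 6.1 makes AOFAS and SF-36 the primary outcomes, and section 3.2.1 sets follow-up at two years.

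**The concern.** Classical repeated measures ANOVA, including the usual SPSS GLM repeated measures procedure, uses only subjects with a value at every level of the visit factor. Suppose a patient completes the surveys at screening, 6-8 weeks and 12 months and leaves at month 13. Section 4.5.1 does not exclude that patient, but the ANOVA does, at all visits. A patient who stays two years and misses one listed survey is treated the same way. The population actually compared is then subjects with no missing listed score through 24 months. That is narrower than the 4.5.1 set and is stated nowhere.

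Two things are at stake. Scores already collected at 12 months and earlier are thrown away. The comparison also becomes conditional on something that happens after randomisation. Section 4.5 allows discontinuation for adverse events or non-adherence, so leaving could be related to outcome and could differ by arm. In that case the arm difference can be distorted even at visits where nothing is missing.

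**Working it through.** **1. The plan's own figure.** Inputs from section 6.5: d = 0.40, two-sided alpha 0.05, independent-samples t-test, 100 evaluable per arm, 15 added per arm. Power comes from the noncentral t distribution with 2n − 2 degrees of freedom and noncentrality d·√(n/2). At n = 100 the noncentrality is 0.40 × √50 = 2.83 and power is 0.804. At n = 99 it is 0.7997. The stated 80% with 100 per arm is reproduced.

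**2. What the allowance covers.** 15/115 = 13.0%. Section 6.5 does not split this into loss before and after 12 months. Under a complete-case analysis it has to absorb early withdrawal, late withdrawal and missed surveys together.

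**3. Complete cases and single-visit t-test power at d = 0.40.** The loss rates are assumptions; the documents give none.

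| Lost before 12 months | Of the rest, lost by 24 months | Per arm at 12 months | Complete per arm | Power with complete cases |
|---|---|---|---|---|
| 0% | 10% | 115 | 104 | 0.819 |
| 0% | 20% | 115 | 92 | 0.770 |
| 5% | 10% | 109 | 98 | 0.796 |
| 10% | 10% | 103.5 | 93 | 0.774 |
| 13% | 5% | 100 | 95 | 0.783 |
| 13% | 10% | 100 | 90 | 0.761 |

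Example: 115 × 0.9 = 103.5, and 103.5 × 0.9 = 93.2.

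Missed surveys act in the same way. If 5% are missed independently at each of the four listed visits, 0.95⁴ = 0.815 are complete, or 115 × 0.815 = 94 per arm. Adding the scheduled 3-month survey gives 0.95⁵ = 0.774, or 89 per arm.

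**4. Which part is avoidable.** For a subject who leaves after 12 months, no method observes the 24-month score. The avoidable loss is at 12 months and earlier, for example 93 used when 103.5 per arm are available.

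**5. Selection bias with no true difference.** Assume a standard normal 12-month score x, correlation 0.6 between visits, and probability of leaving after 12 months p(x) = 1/(1 + exp(−(a + bx))). The mean 12-month score of those who stay is E[x(1 − p)] / E[1 − p]. The bias is the difference in this mean between arms. At the other visits it is 0.6 times as large.

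| Scenario (arm 1; arm 2) | Bias at 12 months | Bias at other visits |
|---|---|---|
| b = 1, 15.5% leave; b = 1, 12% leave | 0.03 SD | 0.02 SD |
| b = 0.5, 10% leave; b = 0, 10% leave | 0.05 SD | 0.03 SD |
| b = 1, 5% leave; b = 0, 5% leave | 0.05 SD | 0.03 SD |
| b = 1, 15.5% leave; b = 0, 12% leave | 0.14 SD | 0.08 SD |

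In the last row a = −2 in both arms, and the stayers' means are −0.137 and 0. The bias is zero if everyone's 12-month and earlier scores are used.

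**The case against.** The strongest reply is that the deletion follows from choices the plan leaves open. The visit list is only an example, and it omits the 3-month survey that the schedule includes. SPSS 24 can fit a mixed model. The per-arm descriptive statistics and the chi-square tests can still include late leavers. If the t-tests in 6.4.1 were applied to scores at a single visit, they would use everyone with a score at that visit. All of this is true. But 24 months is in the list, the SF-36 sentence carries that list into the arm comparison, the model named is repeated measures ANOVA, and the plan does not clearly apply the t-tests to the scores.

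Four stronger readings are tempting, and the documents do not support them.

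- *Two rules in direct contradiction.* Section 4.5.1 keeps late leavers only by implication, and different analyses may have different numbers. What is missing is a rule for incomplete subjects.
- *AOFAS arm comparison certainly affected.* Its two-way sentence names no arms. The point carries over only if an arm comparison is intended, as the stated focus of the primary analysis suggests.
- *The trial's power is 77%.* That is single-visit t-test power under an assumed total loss of 1 − 0.9 × 0.9 = 19%, against an allowance of 13%. It is not the power of the repeated measures analysis. With correlation 0.6 and 93 per arm, the visit-averaged test has about 90% power if d = 0.40 holds at all four visits, and about 68% if there is no effect at screening.
- *A bias of 0.14 SD is to be expected.* It is the least favourable scenario examined. Milder ones give 0.03 to 0.05 SD.

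**Conclusion.** The point stands. As written, the SF-36 arm comparison would most naturally be run on subjects with a score at every included visit. It would discard 12-month and earlier scores from subjects whom 4.5.1 does not exclude, and the plan offers no other way to use them. This rests on the usual reading of repeated measures ANOVA and on 24 months being one of its visits.

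The power cost is modest. Complete cases fall below 100 per arm only when total incompleteness exceeds 13%. The possible bias matters more: 0.03 to 0.14 SD at 12 months, against a design effect of 0.40 SD. At the upper end that is about a third (0.14/0.40 = 0.35). All these sizes depend on assumed loss rates and leaving mechanisms. If leaving is unrelated to outcome, there is no bias and only information is lost. The change should be made, but the finding does not invalidate the design.

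**What to change.** - **Section 6.4.1.** Replace the two-way repeated measures ANOVA for SF-36 and AOFAS with a linear mixed model fitted by REML to all available post-operative scores. Terms: arm, visit, arm-by-visit, the screening score as a covariate and not as a visit level, and the age, gender, BMI and diabetes adjustment already planned. Use an unstructured covariance across visits. SPSS MIXED fits this.
- **Section 6.4.1, AOFAS.** State that the comparison is between arms.
- **Section 6.4.1, incomplete subjects.** State that a later withdrawal or a missed survey does not delete a subject's other visits.
- **Section 4.5.1.** Amend it so that scores collected before withdrawal are not excluded. Changing 6.4.1 alone would put the two sections in conflict, because 4.5.1 would still remove everyone who withdraws before 12 months.
- **Sensitivity analysis.** Add a simple one for departures from missing at random.

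The cost is a paragraph in 6.4.1 and a sentence in 4.5.1, with the same software and no new data. The drawback is reliance on missing at random, although that is generally a weaker assumption than complete-case ANOVA needs.

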4 STUDY PROCEDURES

4.1 Screening Visit

Below is a list of all of the procedures to be performed at each visit.

- Informed Consent
- Physical Exam
- Radiographic/Advanced Imaging
- Medical Record Review
 - Review of the medical record will include reviewing the past medical and surgical history, laboratory values, and most recent visits to other health care providers in the standard fashion of any office or inpatient encounter
- Surgical procedure discussed and operative consent
- Pre-operative AOFAS and SF-36 surveys completed

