6.3 Control of Bias and Confounding

There will be no predilection towards race, ethnicity, sex or sexual orientation. Individuals included in this study will have limited recruit/selection biased. Because the study is focused on physical functionality of patients it will be isolating those patients having a hindfoot fusion procedure and will be recruited from the Foot & Ankle Institute at Western Pennsylvania Hospital, Forbes Regional Hospital, Jefferson Regional Hospital, Bethel Park Surgery Center, and Monroeville Surgery.

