7.3.4 Risk-Benefit Assessment

The risks of immediate weightbearing following foot and ankle surgery are not unlike the risks faced with a traditional post-operative course of non-weightbearing. While there may be a minimal increase in risk for complications in the study group, given the potential increase of stress on the fixation constructs, potential tension to the surgical incision, and potential pain associated with weightbearing immediately after surgery, we believe that the benefits outweigh the risks. Increasing quality of life during the post-operative period, while decreasing debility and returning patients to their pre-injury or pre-surgical state sooner than previously expected is a substantial benefit.

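### Screening AOFAS and SF-36 scores are post-injury for trauma patients but pre-surgical for elective ones, and the visit ANOVAs pool them with no adjustment, which costs power and blurs within-arm change

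*Combined protocol and SAP*

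**What the plan says.** **Population.** The abstract (Setting/Participants) states: "Patients will be eligible if they are undergoing elective or traumatic foot and ankle surgery". Subjects are "identified/recruited during clinic hours as patients requiring an elective or traumatic foot and ankle surgery", so the need for surgery is established before enrolment. Section 6.3 describes a different population: "it will be isolating those patients having a hindfoot fusion procedure". The SF-36 form in the appendix also refers to a hindfoot fusion.

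**Baseline.** Section 4.1 lists "Pre-operative AOFAS and SF-36 surveys completed" among the screening procedures. No recalled pre-injury score is planned. Section 7.3.4 does separate the two reference states when it speaks of "returning patients to their pre-injury or pre-surgical state sooner than previously expected is a substantial benefit".

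**Analysis.** In section 6.4.1 the one-way repeated-measures ANOVA for AOFAS, run within each arm, asks "if the AOFAS scores are significantly different between visits (e.g., screening, post-operative at 6 – 8 weeks, post-operative at 12 months, and post-operative at 24 months". SF-36 has the same one-way analysis, and its two-way ANOVA compares the arms over those same visits. The two-way AOFAS sentence names visits only. Both scores are adjusted for age, gender, BMI and diabetes. Neither the screening score nor elective/trauma status is on that list. Analyses of individual procedures are exploratory, and the allocation in section 3.1 is not stratified.

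**The concern.** One variable carries two meanings. For an elective patient, the screening score describes a chronic state that surgery is meant to improve. For a patient with a fresh fracture or tendon rupture, it describes the days after an injury. The AOFAS form scores support, walking distance, walking surfaces, gait and sagittal motion, and an acutely injured patient can be expected to score low on these. That expectation comes from the items, not from any figure in the documents.

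Two things are at stake:

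- **Interpretation.** A significant within-arm change from screening would partly reflect recovery from acute injury, in a proportion set by case mix.
- **Precision.** In any test that uses screening as a visit level, the elective/trauma gap at baseline becomes unexplained variance, because no term in the model absorbs it.

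**Working it through.** **1. The plan's own figure.** Section 6.5 uses d = 0.40, two-sided alpha 0.05 and 80% power. The normal approximation gives 99 per arm and the exact t calculation gives 100 (power 80.4%). Adding 15 gives 115 per arm. The figure reproduces. It rests on a t-test of questionnaire scores and does not use the baseline.

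**2. Assumed inputs.** The documents give none of these except n and d.
- SD 15 at each visit within each stratum. An effect of 6 points then gives d = 6/15 = 0.40, as in section 6.5.
- Correlation between screening and follow-up of 0.5.
- n = 100 evaluable per arm (section 6.5).
- Trauma share p = 29%, range 10-50%. The data form lists 21 procedures, of which five fracture fixations and Achilles repair make 6/21 = 28.6%. This counts options on a form and is not a case mix.
- Baseline gap G (elective minus trauma) of 20 points, range 20-40, with equal post-operative means in the two strata.

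**3. Shift in pooled within-arm change** = p x G = 0.29 x 20 = 5.8 points, in both arms alike. The range is 0.10 x 20 = 2 to 0.50 x 40 = 20 points.

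**4. Power for an arm contrast on change from screening.**
- Variance of change = 2 x 15² x (1 - 0.5) + p(1 - p)G² = 225 + p(1 - p)G².
- Standardised difference = 6 / (SD of change x √(2/100)).
- Power is by normal approximation.

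| p | G | Variance | SD of change | 6/SE | Power |
|---|---|---|---|---|---|
| any | 0 | 225 | 15.0 | 2.83 | 81% |
| 10% | 20 | 261 | 16.2 | 2.63 | 75% |
| 29% | 20 | 307.4 | 17.5 | 2.42 | 68% |
| 50% | 20 | 325 | 18.0 | 2.35 | 65% |
| 29% | 40 | 554.4 | 23.5 | 1.80 | 44% |
| 50% | 40 | 625 | 25.0 | 1.70 | 40% |

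**5. The two-way ANOVA itself.** This was simulated with screening plus three post-operative visits, 100 per arm, correlation 0.5, an effect of 0.40 SD at every post-operative visit, and 3000 runs. Gaps are in SD units (1 SD = 15 points on the scale above).

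| Trauma share, gap | Arm-by-visit (Greenhouse-Geisser) | Arm main effect, 4 visits | Arm main effect, 3 post-operative visits |
|---|---|---|---|
| no gap | 83% | 77% | 94% |
| 50%, 1 SD | 75% | 75% | 93% |
| 20%, 2 SD | 63% | 73% | 92% |
| 50%, 2 SD | 57% | 71% | 93% |

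With no true effect, the arm main effect rejects in 4.5-5.1% of runs over four visits, and the corrected interaction in 4.4-5.7%. The uncorrected interaction reaches 6.9% in the most extreme setting (50%, 2 SD).

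**6. Post-operative score with screening score and elective/trauma status as covariates.** Residual SD = 15 x √(1 - 0.5²) = 12.99. Then 6 / (12.99 x √0.02) = 3.27, and power is 90% whatever p and G are. Letting the screening slope differ by stratum changes nothing when the baseline SDs are equal. If the trauma baseline SD were 10, power would be 90.2% with a common slope and 90.4% with separate slopes.

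**The case against.** The strongest reply is that the plan does nothing invalid. For a trauma patient the post-injury state is the pre-operative state, and the form has categories for it, including crutches, wheelchair and very short walking distance. Recovery from that state is real change. The shift affects both arms alike, and section 6.4.1 says the primary analysis focuses on the arm comparison. All of this stands. It also rules out several stronger readings that a reader might infer:

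- **That no pre-operative baseline exists for trauma patients.** One exists. What is missing is a pre-injury score, which the plan never claims to collect.
- **That trauma patients score at the floor.** No baseline values are given. A low score need not apply to every injury or to the SF-36 mental scores.
- **That the arm comparison is biased.** Screening precedes the intervention and the gap falls on both arms, so the cost is power.
- **That the sample size in section 6.5 fails.** Its t-test is on scores, not change, and comparisons of post-operative scores keep their power.

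Two further limits apply. The plan names no arm contrast on change from screening, so step 4 illustrates the mechanism and step 5 is closer to the stated analysis. And if section 6.3 governs, trauma patients would be few or absent.

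What the reply does not answer is that screening is a listed visit level, the two-way SF-36 ANOVA uses it, and no covariate separates the two kinds of baseline.

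**Conclusion.** The point holds as a matter of efficiency and interpretation. Followed as written, the plan pools two kinds of baseline in the visit ANOVAs with nothing to absorb the difference. At 29% trauma and a 20-point gap, pooled within-arm change moves by about 6 points and change-from-screening power drops from about 81% to 68%. Under the wider assumptions it runs from about 75% down to 40%. The simulated arm-by-visit test falls from 83% to between 57% and 75%. The main effect over all four visits loses less, and the one over post-operative visits alone loses essentially nothing. These sizes depend on the assumed trauma share, gap, SD and correlation. With no gap, or no trauma patients, the loss disappears. The change is worth making because it is nearly free and the covariate model gains power even when there is no gap.

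**What to change.** In section 6.4.1 and on the data form:

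1. Record elective or trauma status directly as one field. Do not derive it from the procedure, because some procedures (Achilles or peroneal repair, for example) can be either.
2. For the arm comparison, take screening out of the visit factor. Model the post-operative AOFAS and SF-36 scores with the screening score and the elective/trauma indicator as covariates, alongside those already listed. A term for screening score by status is not needed.
3. Label trauma baselines as post-injury, and report within-arm change from screening separately for elective and trauma patients.
4. Reconcile section 6.3 with the eligibility text in the abstract, since the size of the issue depends on which population is enrolled.

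The cost is one form field, one or two model terms, a paragraph of analysis text and a split descriptive table with smaller numbers in each part. The sample size does not change.
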